| Brief Summary | This is a first-in-human, safety and feasibility study of bronchoscopic cryo- immunotherapy (BCI) of peripheral lung tumors in advanced non-small cell lung cancer (NSCLC) and suspected NSCLC. BCI has the potential to stimulate anti-tumor immune responses. Pre- and post-BCI peripheral blood samples will be analyzed to assess for anti-tumor immune responses. Post- BCI peripheral blood will be collected 7 and 14 days after the procedure. Additionally, pre-BCI bronchoalveolar lavage (BAL) specimens will be collected to correlate PD-1 phenotype on pre-BCI BAL lymphocytes by single cell RNA sequencing and BCI-induced anti-tumor immune responses. | | |
| Phase | Phase I | | |
| Objectives Primary: • Establish safety and feasibility of BCI and determine the maximu tolerated dose (MTD) (i.e., freeze duration) Secondary: | | | |
| Assess the extent of BCI-induced anti-tumor immune respons | | | |
| Methodology Dose-escalation trial using a 3+3 design Primary: Feasibility and Safety | | | |
| | Feasibility: successful performance of BCI in at least 80% of participants in whom BCI is attempted Safety endpoints: Dose-limiting toxicity (DLT), defined as incidence of bleeding complications and pneumothorax, length of time to perform BCI, length of fluoroscopy exposure during BCI, and other adverse events | | |
| Endpoints | Secondary: Immune Analysis and Tumor Response Changes in peripheral blood CD8⁺ T cells expressing a combination of Ki67⁺,PD-1+, HLA-DR⁺, CD38⁺, and Bcl-2^{low} after BCI Changes in peripheral blood lymphocyte gene expression after BCI, which will be assessed by the PanCancer OncolmmuneTM profile panel, a 770-plex gene expression panel covering innate and adaptive immune responses (NanoString® Technology, Seattle, WA) Correlation of PD-1 phenotype of pre-BCI BAL lymphocytes by single-cell RNA sequencing and BCI-induced anti-tumor immune responses. | | |
| Study Duration 12 months | | | |
| Participant Duration | 14 days | | |
| Duration of IP administration | BCI will be performed once at the time of a standard-of-care bronchoscopy for another indication. BCI is anticipated to take approximately 15-25 minutes. | | |

| Population | Patients with known or suspected advanced non-small cell lung cancer (stages IIIA/B/C and IVA/B based on the 8th edition TNM staging), with an accessible peripheral lung tumor, and who have been referred to NYU Interventional Pulmonary for bronchoscopy for diagnostic and/or palliative purposes unrelated to this study Patients with high risk clinical features (significant smoking history, history of COPD, presence of spiculated lesion with bronchus sign on chest CT, enlargement of mediastinal/hilar lymph nodes and/or evidence of distant metastatic disease) may be candidates for BCI if they meet all other enrollment criteria. Age: > 22 years of age Gender: All genders ECOG performance status ≤ 2 Location: New York, New York | |
|--------------------------------|--|--|
| Study Sites | New York University Langone Medical Center | |
| Number of participants | Up to 24 participants | |
| Description of Intervention | BCI is performed by advancing a flexible cryoprobe through a bronchoscope to reach a target peripheral tumor. Freeze-thaw cycles will be applied to the target peripheral tumor with the intention of inducing anti-tumor immune responses. The number of freeze-thaw cycles will depend on the size of the target tumor. One freeze-thaw cycle will be applied per one centimeter of largest tumor diameter. Providers will be instructed to remain greater than 2 cm away from critical structures. Freeze times will start at 1 second, and will be increased by dose-escalation protocol based on tolerability. The thaw phase will last until the cryoprobe separates from the target tumor. | |
| Reference Therapy | | |
| Key Procedures | Bronchoscopic Cryo-Immunotherapy Bronchoalveolar lavage in the lobe regions of the primary tumor and of the distal portion of the same lung Pre-BCI (day 0) and Post-BCI (day 7 and day 14 ± 3) blood draws | |
| Statistical Analysis | A standard 3+3 dose escalation design will be implemented. Safety endpoints, including the incidence of bleeding and pneumothorax, will be descriptive. Wilcoxon signed-rank tests will be used to assess paired pre- and post-BCI biomarker levels. | |

Schematic of Study Design

1 Key Roles

Principal Investigator:

[name]

Director, Division of Pulmonary, Critical Care, and Sleep Medicine New York University School of Medicine [name] [contact] [contact]

Additional Investigators:

[name]

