5.6 Duration of Study Participation

The total duration of study participation is 14 days. BCI will be performed at time of standard of care bronchoscopy on day 0. Peripheral blood will be collected by the investigatory team prior to BCI on the day of procedure, which will be drawn off the intravenous catheter inserted for the standard of care bronchoscopy to avoid a separate blood draw whenever possible. The investigatory team will also collect blood samples at approximately 7 days and 14 days after BCI (± 3 days). During each blood

draw, the volume of blood collected will be approximately 2 teaspoons (10 ml). This will occur at routine standard of care follow up clinic visits whenever possible. Alternatively, the investigatory team will collect blood samples at approximately 7 days and 14 days after BCI at the Perlmutter Cancer Center.

Total Number of Participants and Sites

- Total number of participants: 15-24
- Sites: New York University Langone Medical Center

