6.1.2 Dose Escalation Protocol

A standard 3+3 dose escalation strategy will be used. The table below shows the doses that will be provided. Three participants will be initially enrolled at Level 1. If none of the first three participants at a given dose experiences dose-limiting toxicity (DLT), the dose will be escalated. If two or more of the first three participants experience DLT, the prior dose will be deemed the maximum tolerated dose (MTD) and the study will be terminated. If one of the first three participants experiences DLT, an additional three participants will be enrolled at the same dose. If among these six, only one experiences DLT, the dose will be terminated. If two or more of six experience DLT, the prior dose will be deemed the MTD and the study will be terminated. If the MTD is reached and only three participants have been treated at that dose, an additional three will be treated to ensure six subjects are treated at the MTD. DLT are defined in Section 4.1.1 (Primary Study Endpoints: Feasibility and Safety).

| Dose Level | Freeze Time (per site) | Thaw Time |
|------------|------------------------|---|
| Level 1 | 1 second | Will last until the probe separates from target tissue* |
| Level 2 | 2 seconds | Will last until the probe separates from target tissue* |
| Level 3 | 3 seconds | Will last until the probe separates from target tissue* |
| Level 4 | 5 seconds | Will last until the probe separates from target tissue* |
| Level 5 | 10 seconds | Will last until the probe separates from target tissue* |
| Level 6 | 20 seconds | Will last until the probe separates from target tissue* |

CONFIDENTIAL

| Level 7 | 30 seconds | Will last until the probe separates from target |
|---------|------------|---|
| | | tissue* |

6.1.3 **Procedures for Training of Clinicians on Procedural Intervention**

The NYU Interventional Pulmonary service has extensive experience using the flexible cryoprobe for debulking of central airway tumors. BCI will be performed by a board-certified, NYU Interventional Pulmonologist.

Only patients with the presence of a bronchus or airway path leading directly to the peripheral lung tumor will be eligible to undergo BCI. The peripheral tumor will also need to be identified by radial EBUS prior to performing BCI. If the peripheral tumor is unable to be identified by radial ultrasound within 20 minutes, then the patient will not be a candidate to undergo BCI.

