7.1.2 Standard of Care Study Procedures

Pre-BCI screening:

- Medical history (including cancer and cancer treatment history, co-morbidities, functional status, and social history)
- Medication and treatment history (specifically if patient is on a platelet inhibitor other than aspirin
 or anticoagulant), and if patient has previously or is currently receiving chemotherapy, radiation
 therapy, or immunotherapy.
- Physical examination (vital and full physical exam will be performed by clinical team prior to determining patient's fitness for undergoing bronchoscopy
- Chest CT assessment to evaluate for the presence of a bronchus or airway path leading directly to the peripheral lung tumor
- Screening laboratory evaluation as described in Section 7.2
- Pre-BCI blood collection for immune analysis

During bronchoscopy:

• Bronchoalveolar lavage (BAL) will be performed in two locations, which are the regions of the primary tumor and of the distal portion of the same lung. BAL is a standard of care component of routine bronchoscopy for lung cancer.

CONFIDENTIAL

- If there is no pre-existing biopsy-proven non-small cell lung cancer diagnosis, on-site pathology review of a tissue biopsy obtained during bronchoscopy may be performed, if technically feasible or if the patient does not have high risk features for possible non-small cell lung cancer (see above).
- After the standard-of-care portion of the bronchoscopy is complete, the peripheral tumor will need to be identified by radial EBUS. If the peripheral tumor cannot be identified within 20 minutes, then BCI will not be performed.
- BCI will be performed in eligible candidates

Post-BCI:

- Monitor for any adverse events from day 0 to day 7 Post-BCI blood collection for immune analysis on day 7 ± 3
- Post-BCI blood collection for immune analysis on day 14 ± 3
- Patients who undergo BCI and are found not to have non-small cell lung cancer will be monitored for adverse events from day 0 to day 7 and be followed up at a standard of care pose-bronchoscopy visit within 7 ± 3 days. These patients will not have post-BCI blood collected.

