8.4 Study Halting Rules

If 2 or more participants experience DLT at any dose level, then the prior dose will be determined to be the MTD and the study will be terminated. Participants already enrolled in the study will be followed post procedure as per protocol. The study will be terminated in the event of death, massive hemoptysis, or acute respiratory distress syndrome (ARDS).

Additionally, the study will be suspended when three grade 3 AEs determined to be "probably related.". The medical monitor will notify the investigators immediately when the third grade 3 event is reported and enrollment screens will stop accepting new study participants. The investigators will inform the DSMB members within 24 hours of this occurrence and will provide the DSMB with AE listing reports. The DSMB will convene an ad hoc meeting by teleconference or in writing as soon as possible. The DSMB will provide recommendations for proceeding or halting the study.

8.5 Safety Oversight:

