10.4.3 Analysis of the Primary Endpoint: Safety

Safety endpoints will be descriptive in nature, and any possible, probable, or definite adverse event will be counted only once for a given participant. Frequency and severity of all adverse events will be reported, both in the total study population and stratified by dose level.

Dose-limiting toxicities will be tabulated in the whole population and by dose level. Bleeding severity will be graded based on severity scale as described in Section 4.1.1 (Primary Study Endpoints: Feasibility and Safety). Pneumothoraces will be reported and described based on size, associated

CONFIDENTIAL

symptomatology and respiratory impairment, and need for chest tube placement. Length of time to perform BCI and length of time of fluoroscopy exposure during BCI will be reported in minutes. Other adverse events will be recorded and categorized as per the NCI Common Terminology Criteria for Adverse Events (CTCAE) (33).

The maximum tolerated dose (MTD) will be determined based on the dose escalation rules described below and in Section 6.1.1. The MTD is the dose at which fewer than 1 of 3 or at most 1 of 6 participants on that dose experience a DLT.

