10.5 Sample Size

We will aim to enroll approximately 24 patients. The exact number will be determined based on our dose escalation protocol (as described in section 6.1.2).

The table below gives the operating characteristics of this design, presenting the likelihood of escalation when the true DLT rate takes various values. For example, if the true DLT rate is 60%, the probability of escalation is only 0.08. If the true DLT rate is 10%, the probability of escalation is 0.91.

| True DLT Rate | 10% | 20% | 30% | 40% | 50% | 60% | 70% | 80% | 90% |
|---------------------------|------|------|------|------|------|------|------|--------|--------|
| Probability of Escalation | 0.91 | 0.71 | 0.49 | 0.31 | 0.17 | 0.08 | 0.03 | <0.001 | <0.001 |

The small sample size will not provide sufficient power to definitively address the secondary endpoint of measuring BCI induced anti-tumor immune responses. For example, 15 subjects provide approximately 80% power to detect a difference of about 0.75 standard deviations between pre- and post-BCI peripheral blood CD8⁺ T cell expression of PD-1 and Ki67, conservatively assuming a within-subject correlation between assessments of 0.5. However, our results will be critical for informing the design of further studies aimed at estimating response and survival rates with BCI combined with anti-PD1- therapy for the treatment of advanced non-small cell lung cancer.

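### The size limits of 24 and 15–24 are not limits under the 3+3 rules, the 1-in-6 rule in 6.1.2 contradicts the 10.5 table, and one entry in that table is wrong (minor)

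*Combined protocol and SAP*

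**What the plan says.** Trial size is stated three ways.

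- Protocol Summary, number of participants: "Up to 24 participants".
- Section 5.6: "Total number of participants: 15-24".
- Section 10.5: "We will aim to enroll approximately 24 patients. The exact number will be determined based on our dose escalation protocol".

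Section 6.1.2 sets the rules: seven levels and cohorts of three. With 0 of 3 DLTs the dose is escalated, with 1 of 3 three more are added, and with two or more DLTs the trial stops and the prior dose is the MTD. For 1 in 6 it says "If among these six, only one experiences DLT, the dose will be terminated". It also says "If the MTD is reached and only three participants have been treated at that dose, an additional three will be treated", so that six are treated at the MTD.

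Section 10.4.3 counts a dose as tolerated with no DLT in three or "at most 1 of 6 participants on that dose experience a DLT". Section 10.5 tabulates the probability of escalation by true DLT rate, from 0.91 at 10% down to <0.001 at 80% and 90%.

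**The concern.** A maximum, a bounded range and an approximate target are different commitments, and the escalation rules can produce only one set of possible sizes. The rule for 1 DLT in 6 also matters, because it sets both the size and the next dose. If 6.1.2 ends a dose where the 10.5 table assumes escalation, the published operating characteristics belong to a different design from the one in the dosing instructions. At stake are consistent statements of trial size and an unambiguous dosing rule in a first-in-human study.

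**Working it through.** **Step 1. Reproduce the 10.5 table.** Let p be the true DLT rate and q = 1 − p. If escalation follows 0 of 3, or 1 of 3 and then 0 of the next 3, then

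P(escalate) = q³ + (3pq²)(q³) = q³ + 3pq⁵.

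| p | q³ + 3pq⁵ | 10.5 table |
|---|---|---|
| 10% | 0.906 | 0.91 |
| 20% | 0.709 | 0.71 |
| 30% | 0.494 | 0.49 |
| 40% | 0.309 | 0.31 |
| 50% | 0.172 | 0.17 |
| 60% | 0.082 | 0.08 |
| 70% | 0.032 | 0.03 |
| 80% | 0.00877 | <0.001 |
| 90% | 0.00103 | <0.001 |

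The entries from 10% to 70% all match. If 1 in 6 did not escalate, the 10% entry would be q³ = 0.9³ = 0.729, not 0.91. So the table requires escalation after 1 in 6, and 10.4.3 agrees, since it accepts 1 in 6 as tolerable. The 80% entry is wrong: 0.2³ + 3 × 0.8 × 0.2⁵ = 0.0080 + 0.0008 = 0.0088. The 90% entry is only a matter of rounding.

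**Step 2. Count participants.** These are treated participants under 6.1.2, with 1 in 6 escalating.

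- No DLT, Level 7 expanded to six: 7 × 3 + 3 = 24.
- One of Levels 1–6 expanded to six and cleared, then Level 7 at 0 of 3 and expanded: 5 × 3 + 6 + 6 = 27.
- Two or more DLTs in the first three at Level 1: the trial ends at 3.

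So 24 is one path and not a ceiling, and 15 is not a floor. The figure 15 also appears in 10.5, but only in the biomarker power example.

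**Step 3. How often is 24 exceeded?** The documents give no expected DLT rate, so the rates here are assumptions. The 27-participant path above alone has probability 6 × (q³)⁵ × 3pq⁵ × q³ = 18pq²³:

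- p = 2%: 0.36 × 0.628 = 0.226
- p = 5%: 0.90 × 0.307 = 0.277
- p = 10%: 1.80 × 0.0886 = 0.160

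Exact enumeration of every path, with six treated at the MTD, no further step-down and no stops under 8.4, gives:

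| Flat DLT rate | 2% | 5% | 10% |
|---|---|---|---|
| P(N > 24), Level 7 expanded | 0.281 | 0.469 | 0.443 |
| P(N > 27), Level 7 expanded | 0.038 | 0.137 | 0.203 |
| Mean N, Level 7 expanded | 24.7 | 24.6 | 22.0 |
| P(N > 24), Level 7 not expanded | 0.055 | 0.192 | 0.284 |
| P(N < 15), either way | 0.010 | 0.059 | 0.197 |

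With rates rising over the levels as 1, 2, 3, 5, 10, 20 and 30%, P(N > 24) is 0.448 with the Level 7 expansion and 0.362 without.

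The Level 7 rows differ because the protocol leaves the matter open. Section 6.1.2 names an MTD only as the dose below one that failed, while under 10.4.3 a Level 7 at 0 of 3 would qualify as the MTD and so trigger the expansion.

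**The case against.** The strongest reply is that 10.5, the sample size section, already says the right thing: 24 is approximate and the escalation decides. At low DLT rates the mean is close to 24, and most overruns are by one cohort. The design is called a standard 3+3 throughout, so 'terminated' is evidently a slip that staff would read as escalation. All of this stands, and it is why the point is minor. It does not make 24 a maximum or 15 a minimum, and it does not repair the sentence in 6.1.2.

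A reader might go further in four ways that the documents do not support.

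- **That the trial will stop at 24 with a cohort still due.** No rule in 5.8, 6.1.2 or 8.4 stops enrollment at 24. Where Level 7 stands at 0 of 3, 10.4.3 would already let it be the MTD.
- **That the trial may often finish below 15 because 1 in 6 ends it.** Taken literally, 6.1.2 gives P(N < 15) of 0.163, 0.356 and 0.578 at 2, 5 and 10%. Those figures describe a wording error, not the design that 10.5 tabulates.
- **That the trial could run to 42.** Six at every level is arithmetically possible, but the largest probability found in any scenario was below 0.0001. The 8.4 stops, which were not modelled, could only reduce the size.
- **That many more must be enrolled than treated.** It is true that "If the peripheral tumor cannot be identified within 20 minutes, then BCI will not be performed". But 5.1 makes visualization by radial ultrasound an inclusion criterion, and 10.3 analyzes only those treated, so this is largely answered already.

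**Conclusion.** The point holds as a minor one, with three parts wrong as written. First, the 1-in-6 instruction in 6.1.2 contradicts the 10.5 table and 10.4.3. Second, the Summary and 5.6 state limits that the escalation does not respect. Third, the 80% table entry is too small by a factor of about nine (0.0088 against a printed bound of 0.001).

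The size of the second part depends on assumed DLT rates and on whether a clean Level 7 is expanded. For flat rates of 2 to 10%, the chance of passing 24 is roughly 28 to 47% with expansion and 5 to 28% without. At higher rates it falls because the trial stops early: with expansion it is 0.287 at 15% and 0.151 at 20%. As a planning figure, 24 is sound. The table entry changes no dose decision.

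**What to change.** 1. In 6.1.2, change the outcome for 1 DLT in 6 from 'terminated' to 'escalated', and state whether Level 7 is expanded to six when it is cleared at 0 of 3.
2. In the Summary and 5.6, replace the limits with one statement that matches 10.5, for example: *approximately 24 treated participants; the exact number follows the 6.1.2 escalation and may be somewhat more or fewer.*
3. In the 10.5 table, change the 80% entry to 0.009.

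No printed maximum, cap rule or enrolled-count estimate is needed. The cost is wording in three places and one table entry. It adds no participants beyond those the escalation rule behind 10.5 already calls for.

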2.1 Background Information and Relevant Literature

I) Cryoablation and Bronchoscopic Cryo-Immunotherapy (BCI)

Cryotherapy is the local application of extremely cold temperatures for tissue destruction, removal, and/or biopsy. Nitrous oxide is the most commonly utilized cryogen, and provides temperatures below - 40°C at the tip of the cryoprobe(1). In cryoablation, repetitive freeze-thaw cycles cause tissue injury and necrosis. Cryoablation causes cell injury leading to necrosis and apoptosis by multiple mechanisms including formation of intracellular ice crystals (damage cell membranes and organelles), cell dehydration (extra-cellular fluid freezes and the osmolarity of the remaining non-frozen extracellular fluid increases leading to water shifts), and vascular compromise (tissue ischemia from micro-vascular thrombosis)(2-4). Additionally, cryoablation may induce an anti-tumor immune response by causing the release of tumor antigens from dying lung cancer cells, and ultimately stimulating anti-tumor specific T cell activation and proliferation. In contrast, in cryobiopsy and cryoadhesion, target tissue is frozen without a follow-up thaw phase. Frozen target tissue becomes adherent to the cryoprobe to facilitate removal from the airway.

Bronchoscopic cryoablation has been utilized for over twenty years for safe and effective palliative treatment and debulking of endobronchial tumors in the central airways (trachea and proximal bronchi)(5, 6). Percutaneous cryoablation has been utilized for more than a decade to treat peripheral primary and secondary lung tumors that are not amenable to surgical resection(7). However, bronchoscopic cryoablation has not yet been applied to the treatment of peripheral lung tumors. Peripheral lung tumors comprise lung nodules and masses, which are completely surrounded by lung parenchyma. These tumors are located in airways distal to sub-segmental bronchi.

Bronchoscopic cryoablation of peripheral lung tumors is anticipated to induce cytotoxicity to tumor cells. Anti-tumor immune responses are hypothesized to be active against any remaining tumor cells locally, as well as at microscopic and macroscopic distant sites of malignancy. In order to achieve anti-tumor responses, bronchoscopic cryoablation may only need to be performed on a portion of the target tumor. The target tumor will be measured in its largest diameter and one freeze-thaw cycle will be performed per centimeter from the distal portion advancing proximally. This will be referred to as bronchoscopic cryo-immunotherapy or BCI. In the context of treating peripheral lung tumors, the safety profile of BCI is currently unknown, but is anticipated to be safe and well tolerated.

II) Safety Profiles of Current Applications of Cryotherapy in Pulmonary Diseases and Anticipated Safety Profile of BCI

Bronchoscopic cryoablation is an accepted, standard-of-care technique for safe and effective treatment of endobronchial tumors in the central airways. The American Thoracic Society and the American College of Chest Physicians have both endorsed the use of cryotherapy for palliation of central airway obstruction due to inoperable malignant tumors(8, 9). In a review of over five hundred consecutive patients with obstructive tracheobronchial malignant tumors, target tissue was freeze-thawed with a cryoprobe and accessible necrotic tumor material was then removed with biopsy forceps. Cryoprobes of 2.2 mm or 5 mm, depending on target tumor size, were able to safely freeze endobronchial tumors using freeze times of 3 minutes. Complication rates were low, including no reported pneumothoraces and only a four percent rate of post-procedure hemoptysis (6). Overall, hemoptysis improved in 76% of symptomatic patients post-endoluminal cryotherapy.(6) Additionally, early case series using smaller 1.1 mm probes in conjuction with robotic bronchoscopy to biopsy peripheral nodules have not reported significant adverse events (37, 38).

CONFIDENTIAL

Percutaneous cryoablation is also an established approach for the treatment of peripheral primary and secondary lung tumors that are not amenable to surgical resection. In percutaneous cryoablation, rigid cryotherapy probes are inserted via transthoracic CT guidance and the target tumor becomes completely engulfed in an ice ball during freezing. In contrast, in our proposed novel technique of BCI, only a portion of the target tumor will be frozen. Percutaneous cryoablation has been shown to be effective for local tumor control. In percutaneous cryoablation, the target necrotic tumor remains in-situ, and does not undergo any biopsy or tissue removal, which is similar to BCI. In an observational study of over two hundred percutaneous cryoablation procedures of thoracic masses, 86% of masses were reduced or remained stable in size over a six-month period(7). In percutaneous cryoablation of peripheral lung tumors, the cryoprobe must pass through lung parenchyma in order to reach the target peripheral tumor, which carries a significant risk of causing a pneumothorax. In a systematic review of observational studies on percutaneous cryoablation of lung tumors, overall rate of pneumothoraces ranged from 12-62% with up to 17.6% of induced pneumothoraces requiring insertion of thoracostomy tubes(10, 11). In BCI, however, the cryoprobe will reach the target peripheral lung tumor via the airway directly without traversing through the lung parenchyma. Therefore, BCI is anticipated to have a significantly lower risk of pneumothoraces compared to percutaneous cryoablation.

Reports of hemoptysis after percutaneous cryoablation have been small volume and self-limited in the majority of cases (10, 11). For example, in a review of 117 consecutive patients treated with 193 cryoablation sessions of lung tumors, there were no episodes of life-threatening pulmonary hemorrhage (11). However, there have been rare case reports of life-threatening pulmonary hemorrhage previously(12). Post- percutaneous cryoablation hemoptysis may be due to tumor necrosis from freezing or due to lung injury from the cryoprobe traversing through lung parenchyma. In percutaneous cryoablation, cryoprobes with diameters up to 3mm have been used to safely administer freeze times lasting up to 20 minutes 7, 10). In BCI, a smaller cryoprobes of 1.1mm or 1.9mm will administer significantly shorter freeze times based on a dose escalation protocol (see figure). Based on the tolerability of percutaneous cryoablation with non-significant bleeding (if bleeding occurs), significant hemoptysis is not anticipated to occur in BCI. Additionally, the shorter freeze phases, smaller diameter (1.9mm) of the cryoprobe, and avoiding the need for the cryoprobe to traverse through lung parenchyma will further decrease the risk of bleeding in BCI compared to percutaneous cryoablation.

Over the past several years, bronchoscopic cryobiopsy has been studied for the diagnosis of interstitial lung diseases, lung transplant rejection, and peripheral lung lesions, including lung cancer. In contrast to cryoablation, cryobiopsy involves the freezing of target tissue for typically 3-5 seconds without a follow-up thaw phase (13-15). Frozen target tissue becomes adherent to the cryoprobe to facilitate removal via the airway and transport to Pathology for analysis. In observational studies, the rates of pneumothoraces and significant bleeding after trans-bronchial cryobiopsies for the diagnosis of interstitial lung disease and lung transplant rejection are highly variable. For example, in a retrospective review of three hundred consecutive trans-bronchial cryobiopsies for evaluation of interstitial lung disease at a single center, the rates of pneumothoraces and bleeding were 5.0% and 5.2%, respectively(13). In another retrospective review of twenty-five consecutive trans-bronchial cryobiopsies at a single center, the rates of pneumothoraces and significant bleeding (quantified as at least 100cc of hemoptysis post procedure) were 8% and 12%, respectively(14). There are significant differences in technique between our proposed novel procedure of BCI and trans-bronchial cryobiopsy. Most notably, trans-bronchial cryobiopsy does not have a thaw phase and involves the removal of frozen tissue which becomes adherent to the cryoprobe. In BCI, as long as passive thaw phases are of sufficient time to allow for target tissue and cryoprobe to separate, no target tissue will be removed, and significant bleeding and pneumothoraces are not anticipated to occur. For these reasons, BCI of peripheral lung tumors is anticipated to be safe and well-tolerated.

III) Anticipated Feasibility of BCI

CONFIDENTIAL

The feasibility of performing cryobiopsy of peripheral pulmonary lesions with the use of radial endobronchial ultrasound (rEBUS) guidance has been previously demonstrated (16). In a prospective study of thirty-eight consecutive subjects with peripheral lung lesions of less than four centimeters (excluding one patient with a visible endobronchial tumor), thirty-one peripheral lesions were identified by rEBUS. The average time duration for tumor detection by rEBUS was 7.6 minutes. All thirty-one peripheral lesions underwent transbronchial cryobiopsies successfully. Based upon these experiences, the utilization of rEBUS to guide BCI of peripheral lung tumors is anticipated to be technically feasible (16).

IV) Proposed Mechanism for BCI Inducing Anti-Tumor Immune Responses

BCI is anticipated to induce anti-tumor immune responses. Cryo-immunotherapy involves the killing of tumor cells by freezing, generating an "*in-situ* vaccination" associated with CD8+T cell activation and proliferation, which has been confirmed in murine models as well as in early-phase human clinical trials(17). A proposed mechanism is that cryoablation may, in part, induce the release of tumor antigens from dying lung cancer cells. These released tumor antigens will be taken up by antigen presenting cells, which may interact with T cells and lead to anti-tumor specific T cell activation and proliferation.

BCI induced anti-tumor immune responses may be further enhanced in combination with other treatments. Cryoablation combined with other therapies have demonstrated enhanced anti-tumor immune responses, slower tumor growth, and have been associated with improved outcomes compared to treatments without cryoablation in pre-clinical and experimental clinical trials of non-small cell lung cancer (18-21). We are particularly interested in the possibility of combining BCI with anti-PD-1 monoclonal antibodies and other checkpoint inhibitors for the treatment of advanced non-small cell lung cancer. Synergistic effects of BCI and immune checkpoint inhibitors (ICI) may enable tumor responses in patients refractory to treatment with ICI alone.

V) BCI Combined with Immune Checkpoint Inhibitors

Immune checkpoint inhibitors (ICI) have emerged as first-line treatment in select patients with advanced non-small cell lung cancer who have tumor PDL-1 expression of greater than 50% (22). However, only approximately twenty percent of patients with non-small cell lung cancer respond to ICI in the majority of clinical trials (23). Individual response to ICI therapy in advanced NSCLC is affected by PD-1/PD-L1 expression and the presence of T cell infiltration within the tumor microenvironment (24). One strategy to increase ICI response in advanced NSCLC would be to combine ICI with other modalities capable of stimulating tumor-specific T cell responses in the tumor microenvironment such as BCI. BCI may increase the presence of activated, tumor-reactive CD8+ T cells within the tumor microenvironment and peripheral blood, and may ultimately improve clinical responses to ICIs.

The combination cryoablation and ICI has demonstrated enhanced immune responses in the treatment of a murine prostate cancer model and in a phase I clinical trial in breast cancer (25, 26). In a murine prostate cancer model, prostate tumor cryoablation combined with an anti-CTLA-4 monoclonal antibody (Mab) resulted in growth inhibition, greater CD4⁺ and CD8⁺ T cell infiltration, and higher T effector to T regulatory cell ratios in distant prostate tumors compared to cryoablation or anti-CTLA-4 MAb alone (25). A phase I clinical trial of neoadjuvant cryo-immunotherapy in breast cancer demonstrated that the combination of percutaneous cryoablation and ipilimumab was safe and associated with increased expression of CD4⁺ and CD8⁺ T cell activation markers (e.g. ICOS and Ki67) in peripheral blood mononuclear cells (26). The combination of cryoablation and immune checkpoint inhibitors is currently being investigated for the treatment of non-small cell lung cancer in a clinical trial based at Brown University (ClinicalTrials.gov identifier: NCT02469701).

VI) Biomarkers to Assess for BCI Induced Anti-Tumor Immune Responses

There is no well-established peripheral blood biomarker panel to assess for immune responses after cryo-immunotherapy. After percutaneous cryoablation, previous studies have not demonstrated meaningful changes in total lymphocyte counts in peripheral blood, suggesting that biomarkers of cryoablation-induced immune responses lie within finer subsets of lymphocytes. Consistent with this, Lin, et al. recently reported that IL-2 and IFN-gamma were elevated in serum after cryoablation (25), suggesting that changes in T-cell function may follow the procedure. Assays of secreted cytokines in serum, however, fail to identify the exact cell type producing the cytokines, and these cytokines can be released by non-T-cells. Moreover, tumor-specific T-cells are capable of expressing many cytokines other than IL-2 and IFN-gamma, each of which provides different mechanistic information about the nature of the immune response. Therefore, cellular assays that combine global markers of T-cell activation with cell-by-cell analysis of many different cytokines will be required to determine if cryoablation induces T-cell responses. Additionally, given the rationale and potential for combining cryoablation and checkpoint inhibitor therapies, an analysis of checkpoint molecule expression will also be valuable in this setting.

Recently, a co-investigator on this study ([name], Director of Precision Immunology Incubator at NYU Langone Health) developed 30+ parameter flow cytometry technology (which has now been commercialized by BD Biosciences as the Symphony A5). This technology is ideally suited to the analyses described above, because of the bright fluorescent dyes used (Brilliant Dyes, BD Biosciences)

| Panel 1 | Panel 2 |
|-----------|------------|
| CD45 | CD45 |
| Live/Dead | Live/Dead |
| CD3 | CD3 |
| CD4 | CD4 |
| CD8 | CD8 |
| CD45RO | CD45RO |
| CCR7 | CD154 |
| CD27 | CD107A |
| CD28 | IFNG |
| CD127 | IL2 |
| CD57 | TNF |
| CD25 | IL3 |
| CD95 | IL4 |
| CD69 | IL5 |
| CD103 | IL8 |
| CXCR6 | IL9 |
| CXCR3 | IL10 |
| BTLA | IL13 |
| TIGIT | IL17 |
| CTLA4 | IL21 |
| 4-1BB | GMCSF |
| 2B4 | RANTES |
| GITR | LTA |
| TIM3 | BCL2 |
| ICOS | KI67 |
| PD1 | PD1 |
| TIGIT | CD38 |
| HLA-DR | HLA-DR |
| OX40 | Granzyme B |
| CD69 | CD69 |

and the low electronic noise of the system. (The technology provides better resolution than alternate cytometry technologies, like mass cytometry (CyTOF), with higher throughput, less cell loss, and a more robust hardware platform.) [name] developed a number of antibody staining panels for the system, including a panel that assesses many immune checkpoint molecules at once, and a pan-cytokine/global T-cell activation panel. Table 1 lists the markers studied with each panel. There are three notable advantages of highly multiplexed flow cytometry panels like these. First, they allow broad screening of many markers in order to find the most sensitive biomarkers in a particular disease setting. Second, by finely and precisely characterizing combined expression of every marker studied at the single cell level, a more detailed, mechanistic understanding of responses is possible than with serum, secretion, or bulk population assays. Finally, the technology is sample sparing; it provides maximal information (about protein expression) from a single vial of cells; this will be important given the relatively low numbers of cells collected from BAL. Though a number of institutions now have high-parameter flow cytometry technology, these panels have not been successfully developed elsewhere, and those institutions do not have [name] expertise in application of this technology.

Although this approach is novel in immuno-oncology, there is precedent, particularly from studies of vaccine responses. In healthy individuals, baseline peripheral blood CD8⁺ T cell HLA-DR⁺CD38⁺ and Ki67⁺Bcl-2^{low} expression is 0.5-2% and less than 0.5%, respectively (26). After immunization of healthy volunteers with the smallpox vaccine, up to 40% of peripheral blood CD8⁺ T

cells displayed HLA-DR⁺CD38⁺Ki67⁺Bcl-2^{low} (26). Similarly, in 29 patients with advanced NSCLC started on PD-1/PDL-1 axis inhibitory antibodies, approximately 70% of patients had a 1.5-fold increase in peripheral blood Ki67⁺CD8⁺ T cells demonstrating high levels of expression of DR⁺CD38⁺ Bcl-2^{low} and PD-1 post-treatment (27). Approximately 25-80% of these responding Ki67⁺CD8⁺PD-1⁺T cells expressed intra-cellular granzyme B, consistent with cytotoxic potential (27). Epstein-Barr Virus (EBV) -specific CD8⁺T cells had minimal activation and proliferation after PD-1 targeted therapy suggesting these CD8⁺

CONFIDENTIAL

T cell responses may be tumor specific (27). Importantly, 80% of patients who developed these CD8⁺ T cell responses within 4 weeks of starting anti-PD-1 therapy had a clinical benefit.

In addition to assessing for pan-cytokine/global T cell activation and expression of immune checkpoint molecules in peripheral blood mononuclear cells utilizing flow cytometry technology, the NanoString[™] can assess for a variety of other immune biomarkers from peripheral blood. The NanoString[™] platform offers the convenience of straightforward high-throughput mRNA quantitation using RNA barcodes to probe and count mRNA transcripts of interest (28). The pre-designed OncoImmune[™] Profile panel, which measures 770 gene targets most relevant in tumor immunobiology.

